Successful completion of our proposed pilot study addresses a critical knowledge gap in the treatment of chronic plantar fasciitis and breaches the translational roadblock of clinical implementation. The results from this rigorous pilot study will provide the framework for our anticipated full-scale efficacy trial with the potential of affording the clinician an upgraded evidenced-based treatment option that has been demonstrated to be safe, effective, and reproducible.

Objectives

1. Assess feasibility of infracalcaneal peppering injection technique with and without CSI in the management of patients with chronic plantar fasciitis.
 - a. Feasibility of recruitment, randomization, retention, patient and physician time constraints, and tolerability of treatment will be assessed. Clear quantitative benchmarks and a number needed to treat will be achieved for planned utilization in a subsequent full-scale efficacy trial.
2. Assess the efficacy of infracalcaneal peppering injection with and without CSI for reduction in pain utilizing two validated patient reported outcomes measures (PROMs): the Visual Analog Scale (VAS) and Foot Function Index (FFI), administered at baseline, then at 2, 4, 8, and 12 weeks. Minimal Important Difference (MID) calculations for both VAS and FFI PROMs, specifically for plantar fasciitis, have already been investigated/established and will be used as a reference.
 - a. Greater than 75% of these PROMs from ALL cumulative target dates will be captured, providing a target number needed to treat (NNT) to conduct a full-scale efficacy trial investigation.

Methods and Measures

Design: A randomized, double-blind placebo-controlled pilot study at one single institution

Setting: Atrium Health Wake Forest Baptist Department of Orthopaedic Surgery-Podiatry Services practice located in High Point, North Carolina

Subject Selection Criteria

Inclusion Criteria

- Men and women 18 years of age and older
- Patient reported history of plantar heel pain *and* confirmed clinical tenderness of pain with direct palpation of the medial calcaneal tubercle on baseline exam
- Diagnosis of chronic plantar fasciitis, defined for study purposes as symptoms greater than or equal to 6 weeks in duration

Exclusion Criteria

- Individuals less than 18 years of age
- Pregnancy

- History of receiving a local heel injection (i.e. CSI or other injectate) within the last 3 months
- Prior heel trauma or surgery
- Allergy to local corticosteroid or local anesthesia

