
Sample Size

We estimate the sample size required to answer the research question to be 50 participants.

Interventions and Interactions

Once both informed consent and enrollment have been verified, initial evaluation by the PI will be conducted on participants, and baseline assessments will be performed. The assessments include:

- Documentation of participant age at enrollment along with information on sex/gender, race, and ethnicity to ensure the study involves Inclusion of Individuals across the Lifespan
- History and physical exam
- Calculated BMI
- Documentation of referral patterns (PCP, self, or other referral)
 - If from PCP or other, documentation of what information/work-up was provided (e.g. told they have “heel spur”, given NSAIDs, exercises, etc.)
- Clinical confirmation/diagnosis of plantar fasciitis (pain at medial calcaneal tubercle)
- Dolorimeter readings of PPT # (pressure algometer)
- Documentation of subjective reporting of first-step pain (yes/no)
- Foot posture score
- Heel tenderness score
- Initial X-ray (notation and measurement of heel spur) of the symptomatic foot/heel will be performed, if not already completed
- Initial diagnostic musculoskeletal US (PF thickness and echogenicity; fat pad thickness)
- Patient completed baseline self-assessment of both “general heel pain” and “first step pain” (VAS PROM)
- Patient completed baseline self-assessment of foot function (FFI PROM)

At this point, the patient will be block allocated to their study arm, having been randomized in a double-blind fashion by the clinical coordinator. This individual will facilitate safe record-keeping and the processes required to maintain the double-blind design of this study. We will specifically conduct the study in a permuted block design to ensure a 1:1 ratio for the two treatment intervention groups. The study arms are as follows:

- Group 1 - CSI/LA injection
- Group 2 - LA/Saline injection

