Study Visit #4 – 8 weeks post-treatment intervention	No payment. Next payment at 12-week follow-up study visit (visit #5).
Study Visit #5 – 12 weeks post-treatment intervention	\$40.00

Analytical Plan

Results will be analyzed initially using descriptive statistics. Comparison between groups will be done using chi square tests for proportions, and t-tests or ANOVA procedures for continuous variables. Regression analysis will be performed to identify independent outcome predictors. Other inferential statistical analysis will be conducted as appropriate.

Human Subjects Protection

All patients ages 18 years and up with a diagnosis of plantar heel pain will be screened for inclusion into the study. The study will be conducted in accordance with the current IRB-approved clinical protocol; ICH GCP Guidelines adopted by the FDA; relevant policies, requirements, and regulations of the clinical test site IRB; and applicable federal agencies.

Patients who meet the inclusion criteria will be asked to participate in the research study and provided ample time and encouragement to ask questions and discuss the study with others (medical providers, family, friends, etc.). A copy of the informed consent form will be provided to the patient. The study team will answer all questions.

Subjects may withdraw from the study at any time for any reason at their request. Otherwise, participants will be followed as per the protocol. Attempts will be made to collect clinical data from withdrawn subjects. There will be no replacement of subjects who withdraw from the study.

Subject Recruitment Methods

The study will recruit patients who present to the Atrium Health Wake Forest Baptist Department of Orthopaedic Surgery-Podiatry Services practice located in High Point, North Carolina with symptoms of plantar heel pain. In order to approach patients that have received care at this practice in the past, we will create an i2b2 query to result a list of patients seen by [name] and diagnosed with plantar fasciitis within the last 3 years (11/1/2020 – 11/1/2023). These patients will be contacted by the study coordinator to introduce the study, gauge their interest, and begin the pre-screening process if they opt in to doing so.

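### VAS, FFI, pressure threshold and tenderness are measured at four follow-ups but compared only by t-tests or ANOVA; a mixed model would use every score, with a modest gain over per-visit t-tests and a large one over listwise ANOVA

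*Combined protocol and SAP*

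**What the plan says.** Objective 2 has the two patient-reported measures "administered at baseline, then at 2, 4, 8, and 12 weeks". The visit descriptions and the Evaluation Schedule Summary put pressure threshold and heel tenderness score at the same follow-up visits.

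The Analytical Plan is one short paragraph. After descriptive statistics it gives chi-square tests for proportions and "t-tests or ANOVA procedures for continuous variables". It then adds "Regression analysis will be performed to identify independent outcome predictors" and "Other inferential statistical analysis will be conducted as appropriate". It names no longitudinal model, main visit, baseline adjustment, analysis population or rule for missed visits.

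On completeness, Objective 2a says "Greater than 75% of these PROMs from ALL cumulative target dates will be captured". Human Subjects Protection allows withdrawal at any time and adds "Attempts will be made to collect clinical data from withdrawn subjects" and "There will be no replacement of subjects who withdraw from the study".

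**The concern.** The same patient supplies up to four follow-up values per outcome. With two arms, a one-way ANOVA at a visit is the t-test (F = t²), so the named methods have two natural readings. One is a separate test at each visit on whoever attended. The other is a classical repeated-measures ANOVA, which needs all four follow-ups from every patient it keeps.

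The first reading makes no use of the baseline value, or of what is already known about a patient who misses the visit being tested. The second throws away scores that patients did supply. The plan does not say which applies, and their costs differ greatly. With 50 patients, no replacement, and efficacy as the second objective, either loss is avoidable.

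**Working it through.** **Inputs from the documents.** N = 50 (Sample Size), 1:1 allocation, four follow-ups, PROM capture above 75%. The protocol gives no alpha, power, effect size, SD or dropout for the 50, so that figure cannot be reproduced; it is used here only as a head count.

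**Assumptions.** Equal variance at each visit and equal correlation ρ = 0.5 to 0.7 between any two follow-ups. Two missingness patterns: visits missed independently (75% or 90% captured), or permanent dropout of 10% or 15% at each visit after week 2.

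**Patients kept.**
- Scattered misses: week-12 t-test 50p; all four follow-ups 50p⁴. At p = 0.75: 37.5 and 50 × 0.316 = 15.8. At p = 0.90: 45.0 and 50 × 0.656 = 32.8.
- Dropout h per visit: both are 50(1−h)³. For h = 0.10: 50 × 0.729 = 36.5. For h = 0.15: 50 × 0.614 = 30.7. Overall capture is (1 + 0.9 + 0.81 + 0.729)/4 = 86% and (1 + 0.85 + 0.7225 + 0.614)/4 = 80%.

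**Mixed-model information.** For each attendance pattern m with probability w, let K pick out the attended visits from the 4 × 4 covariance Σ. Then I = Σₘ w K′(KΣK′)⁻¹K and V = I⁻¹. With unit variance, the effective N for week 12 is 50/V₁₂,₁₂, where V₁₂,₁₂ is the week-12 diagonal entry. The week-12 SE ratio is √(effective N ÷ N with week 12). The last column takes the square root of the variance ratio for the four-visit average.

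| Pattern | N with week 12 | N complete | Mixed-model effective N, week 12 | Week-12 SE: t-test ÷ mixed model | Averaged SE: listwise ANOVA ÷ mixed model |
|---|---|---|---|---|---|
| Scattered, 75% | 37.5 | 15.8 | 40.9–43.8 | 1.04–1.08 | 1.70–1.74 |
| Scattered, 90% | 45.0 | 32.8 | 46.7–47.9 | 1.02–1.03 | 1.22–1.23 |
| Dropout 10% per visit | 36.5 | 36.5 | 40.0–43.0 | 1.05–1.09 | 1.13–1.15 |
| Dropout 15% per visit | 30.7 | 30.7 | 35.1–39.3 | 1.07–1.13 | 1.21–1.24 |

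Example: √(40.9/37.5) = 1.04. If correlation instead decays with time (AR(1), same ρ), the week-12 ratios fall to 1.01–1.06. These are large-sample figures with the covariance treated as known, so the gain over the t-test would be slightly smaller with 50 patients.

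**Baseline.** If baseline correlates with week 12 at the same ρ, adjustment multiplies the variance of the raw week-12 score by 1 − ρ² = 0.75 to 0.51. An unadjusted t-test then has an SE 1/√0.75 = 1.15 to 1/√0.51 = 1.40 times larger. This does not multiply with the table: after conditioning on baseline, the correlation left between follow-ups is ρ/(1+ρ) = 0.33 to 0.41, so earlier scores recover less.

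**Bias.** Assume an SD of 25 mm, dropout that depends on the last VAS, an early steroid benefit and no true week-12 difference. In simulation the week-12 t-test was off by 0.9 to 1.4 mm, and the likelihood estimate was within 0.1 mm of zero. With 15 to 18 patients left per arm, the SE is 25√(2/18) = 8.3 to 25√(2/15) = 9.1 mm, so the bias is roughly 0.1 to 0.2 SE.

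**The case against.** Several points on the other side stand.

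- Per-visit t-tests use every score collected at each visit; someone absent at week 8 still counts at weeks 2, 4 and 12. On this most literal reading the loss is the table's 2% to 13%, and the bias is small against its SE.
- The plan never uses the term repeated-measures ANOVA, so the large losses belong to an inferred option. They are largest when misses are scattered. That pattern is plausible, because Patient Retention pays nothing at weeks 2 and 8, but it is not stated.
- The regression sentence and the open clause leave room for a mixed model. They do not specify one: regression is reserved for predictors, and the open clause defers the choice until after the data are seen.
- A baseline-adjusted ANCOVA at a named visit would also be defensible and would capture the baseline gain. It would still ignore the earlier scores of patients missing that visit.
- The likelihood estimate is unbiased above because the simulated data were missing at random. That is an assumption about the trial.

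A reader might infer three stronger things that the documents do not support:

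- **That patients will be deleted.** The 75% figure is a minimum target, not a forecast. Reminders, staged payments and attempts to collect data after withdrawal all work against missed visits.
- **That visits will be pooled as independent rows, inflating the type I error.** Nothing in the plan suggests this.
- **That the pilot's effect and SD are to be carried into the full trial.** The Objectives speak of quantitative benchmarks and a number needed to treat. A mixed model of mean scores does not supply the latter; it needs a responder definition of its own.

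**Conclusion.** The concern holds in a limited form. For outcomes measured four times after baseline, the only named between-arm methods ignore baseline and earlier scores (per-visit tests) or delete incomplete patients (classical repeated-measures ANOVA). A better method is available at almost no cost.

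Under the equal-correlation assumption (0.5 to 0.7), per-visit t-tests cost about 2% to 13% in week-12 SE, before baseline adjustment, plus a bias of about 1 mm under the assumed dropout mechanism. Listwise ANOVA costs a factor of about 1.2 to 1.7 in the SE of the visit-averaged difference with scattered misses at 75% to 90% capture, and 1.13 to 1.24 with dropout of 10% to 15% per visit. Correlation, SD and missingness pattern are assumptions; the documents give only N, the visits and the capture target. The change should be made before analysis, but the study does not depend on it: this is a pilot whose first objective is feasibility.

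**What to change.** In the Analytical Plan, replace the t-test/ANOVA sentence for both VAS items, FFI, pressure threshold and tenderness score with wording to this effect:

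*Each repeated outcome will be analysed by one linear mixed model fitted by REML to all randomised patients with at least one follow-up value, without listwise deletion. Fixed effects are arm, visit, arm-by-visit and baseline value. Within-patient covariance is unstructured, with compound symmetry if that does not converge, and Kenward-Roger degrees of freedom. The arm difference and 95% confidence interval will be reported at each visit; week 12 is the main contrast.*

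The schedule marks these measures at both screening and the injection day, so the text must say which is baseline. Keep the t-test for outcomes with a single follow-up, such as ultrasound. Add a short sensitivity analysis for data not missing at random.

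Cost: a few lines of plan and code, slightly more analysis work, and reliance on missing-at-random for the main result. No new patients, visits or data are needed.

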Appendix

1. Data Collection Sheet
2. VAS PROM
3. FFI PROM
4. Exercise Diary
5. Exit Survey
